4.4.3. Study Sites

We will conduct the trial in community-based primary care practices in North Carolina, chosen to reflect diversity in geography and populations served. Practices will be affiliated with the Wake Forest Health Network (**Table 2**). Pilot data from target clinic systems show significant diversity in terms of payer mix (7%-10% Medicaid vs 48%) and racial diversity (76%-83% white). To increase racial diversity further, we will selectively enroll clinics with greater diversity. Counties where the clinics are located range from rural to urban. No currently identified clinics use tablet devices with patients, and we will exclude any additional clinics that already use tablets. Each potential study clinic will complete a baseline clinic overview questionnaire (Appendix B). Data from this questionnaire will be used to construct our final study clinic sample. All clinics will receive at least one study iPad (preloaded with mPATH) per full-time equivalent clinician. All clinics will keep the study iPads at the end of the study, encouraging participation.

4.4.4. Study Cohort

mPATH is designed to be given to all English or Spanish-speaking patients on clinic check-in. Therefore, our implementation outcomes cohort will include all adult (18 and over) English or Spanish-speaking patients who are seen in the study clinics in the 12 months following the initial clinic mPATH launch date. Our effectiveness outcome will include all English or Spanish speaking patients aged 50-74 who are eligible for CRC screening based on EHR records in the 12 months prior to and 12 months following the initial clinic mPATH launch date. We can capture all data needed for this cohort because all the clinics have searchable electronic health records.

4.4.5. Implementation and Clinic Randomization

We will randomly implement mPATH-CRC in 2 clinics (1 “high touch” and 1 “low touch”) until all 22 clinics are enrolled. To control for major organizational differences that could impact implementation, we will first select 2 clinics of similar size, then randomly assign one to receive the “high touch” strategy and the other the “low touch” strategy.

4.4.6. Data Collection

Baseline clinic personnel survey (Appendix B): At the initial kick-off training visit, we will administer a baseline survey to all clinic personnel (e.g., administrators, nurses, providers) who are involved with the implementation of mPATH-CRC, as identified by the local clinic champions. All surveys will assess constructs of the Technology Acceptance Model and the Dynamic Sustainability Framework.^{56,69} Clinic personnel who do not complete the baseline survey (i.e., new hires) will complete it with their first follow-up survey (described below).

Follow-up clinic personnel survey (Appendix B): Because clinic environments and experience with the mPATH system will evolve over time, we will administer a follow-up survey 6 months and 12 months after the initial on-site training. If a clinic site decides to stop using the mPATH program prior to a scheduled follow-up survey, one final follow-up survey will be administered within 6 weeks of the practice discontinuing use of mPATH. The follow-up survey will assess organizational characteristics, individual characteristics, and experience with the mPATH-CRC system. Each person will receive a \$10 incentive for each survey completed.

Clinic Contact and Cost Database (Appendix B): All study team contact with the clinics, and all technology costs associated with implementing and maintaining mPATH will be recorded in a secure, electronic database. Data will include date of contact, mode of contact (i.e., in-person,

EFFECTIVENESS AND IMPLEMENTATION OF MPATH-CRC: A MOBILE HEALTH SYSTEM FOR

COLORECTAL CANCER SCREENING

Wake Forest Baptist Comprehensive Cancer Center (WFBCCC)

WFBCCC # TBD

phone, email), person initiating contact, purpose of contact, and the roles of staff involved in the contact. These data will allow us to compare the cost of the “high touch” and “low touch” intervention strategies and associations between the amount of support given and specific implementation outcomes.

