4.4 Implementation Trial

In a randomized-controlled cluster study of 22 primary care clinics, we will compare the implementation outcomes (as defined by the RE-AIM framework)⁶⁶ and implementation costs of the “high touch” strategy to a “low touch” strategy. The components of each strategy and their timing are outlined in **Table 1**.

4.4.1. “High Touch” Implementation Strategy

The “high touch” strategy consists of pre-implementation activities, training, and ongoing support.

Table 1. Comparison of Implementation Strategies

| High Touch Strategy | Low Touch Strategy |
|--|--|
| | Pre-Implementation Activities |
| 
• Clinic champion identified | 
• N/A |
| | Implementation Kick-Off |
| 
• On-site training with key clinic personnel• On-site training with providers• At elbow support on day of launch | 
• On-site training with key clinic personnel |
| | Months 1 – 6 |
| 
• Phone/email technical support, as needed.• Access to QA data• Scheduled phone-calls with clinic champion to review QA data and explore potential barriers.• Additional on-site trainings as requested.• Monthly “shout-out memos” highlighting staff performance | 
• Phone/email technical support, as needed• Access to QA data |
| | Months 7 - 12 |
| 
• Phone/email technical support, as needed | 
• Phone/email technical support, as needed |

Red text indicates items unique to High Touch Strategy

Pre-implementation activities. At each site, we will identify a clinic champion who will guide the local implementation effort. Champions typically arise through self or peer-nomination.⁶⁷ This person typically plays a central role in implementing new systems and has a demonstrated ability to communicate effectively, navigate the organizational environment, promote a project, and work well with others.^{67,68} We will identify the champion by asking clinic administrators, lead nurses, and lead physicians who meets these qualities and would be willing to serve in this role. Each champion will then help the team identify a nursing super-user and a front desk super-

EFFECTIVENESS AND IMPLEMENTATION OF MPATH-CRC: A MOBILE HEALTH SYSTEM FOR

COLORECTAL CANCER SCREENING

Wake Forest Baptist Comprehensive Cancer Center (WFBCCC)

WFBCCC # TBD

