user. Lastly, each clinic will identify an alternate champion to assist with implementation and provide continuity if the champion is unavailable due to vacation or illness. The alternate champion may be one of the super-users. We designed mPATH for use by patients before medical visits, but the timing and location of use can vary. However, each clinic may adjust the implementation to meet their unique needs.

Kick-off training session. Two members of the study team will visit each practice to conduct a training session for clinic staff identified by the local clinic champion. This training will include hands-on practice with mPATH, including scenarios where patients “self-order” tests, to increase staff’s comfort with the program, increase their self-efficacy, and demonstrate its usability.

A separate brief training session will be held for the clinic providers. The provider training will include an overview of the mPATH program and its functionality. Because providers will not directly interact with the mPATH program, the provider training will not include hands-on practice scenarios.

At-elbow support. The study team will provide at-elbow technical support the day the clinic launches mPATH in their practice.

On-Going Support: The study team will conduct a conference call with the clinic champion and alternate 2-3 business days after the launch date, and then at weeks 2, 4, 8, 16, and 24 post-launch to discuss the clinic’s experiences with mPATH, review QA reports generated from mPATH data (frequency of use, patient demographics), explore the need for adaptations, and provide support. If program usage is below goal levels, barriers will be reviewed with the clinic champion and additional on-site training offered. Clinics may request technical support and additional training at any time, and clinics can self-generate reports to self-monitor mPATH-CRC implementation.

4.4.2. “Low Touch” Implementation Strategy

Clinics randomized to receive the low touch implementation strategy will receive: 1) the initial kick-off on-site training session and implementation materials (identical to the “high touch” group), and 2) access to phone/email technical support as requested. No adaptations will be made to the

mPATH program for “low touch” clinics, nor will study staff proactively reach out to them after the kick-off training session.

Table 2. Characteristics of study clinics

| | WFCP | Cornerstone | KY |

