4.6 Mixed-Methods Study

The mixed-methods study will examine the facilitators and barriers to maintenance (sustained use of mPATH-CRC over time). In the 12th month after each clinic’s launch date, we will identify sites who have maintained use of the mPATH program throughout the study period. To supplement the quantitative data gathered with our clinic surveys (Section 4.4.6), we will conduct semi-structured interviews with four members of each clinic: the clinic champion, one clinician, one front desk team member, and one medical assistant/nursing team member. The clinic champion will assist in the identification of the other team members for interviews based on their experience with the mPATH program. All participants will receive a \$50 gift card. Using an interview guide (Appendix C), we will explore how mPATH-CRC was incorporated in the clinic’s work flow and factors that affected maintenance such as intervention adaptations, organizational characteristics, and the champion’s role. There will be a separate version of the interview guide for clinics who have very low (or no) usage of mPATH during their participation in the study.^{56,69,70} Members of clinics that opt to discontinue use of mPATH will be interviewed as soon as practical after they discontinue use. We will interview representatives from study clinics until thematic saturation is reached. These semi-structured interviews, expected to last approximately 30 minutes, will be conducted by phone or video conference and analyzed by staff trained in qualitative methods. Interviews will be audio recorded and transcribed verbatim. Transcripts will be imported into ATLAS.ti software,⁷¹ iteratively reviewed, coded by concept, and analyzed thematically to describe the implementation and sustainability experience. Themes will be compared among clinics to determine any differences.

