5.3 Secondary Outcomes

- 5.3.1 mPATH™-CRC Reach (by month): The proportion of patients aged 50-74 who are eligible for CRC screening who complete mPATH™-CRC or have risk factors identified by mPATH™-CheckIn in months 1-5 following implementation
- 5.3.2 mPATH™-CRC Reach (by socioeconomic strata): The proportion of patients aged 50-74 who are eligible for CRC screening who complete mPATH™-CRC or have risk factors identified by mPATH™-CheckIn in months 1-6 by socioeconomic strata; this outcome will also be calculated among CheckIn users only
- 5.3.3 mPATH™-CRC Adoption: The mean usage of mPATH™-CRC among staff and providers over the first 6 months following implementation; usage is calculated for each staff/provider as the proportion of times mPATH™-CRC is completed out of the total times mPATH™-CRC should have been launched.
- 5.3.4 mPATH™-CRC Acceptability, Appropriateness, and Feasibility: Mean Acceptability of Intervention Measure (AIM), Intervention Appropriateness Measure (IAM), and Feasibility of Intervention Measure (FIM) scores (68) for mPATH™-CRC as assessed on the 6-month clinic personnel survey
- 5.3.5 mPATH™-CRC Implementation Fidelity: The proportion of patients who use mPATH™-CRC and request a CRC screening test who have a test ordered or have the order dismissed (i.e., “self-order” feature is used as designed) in months 1-6
- 5.3.6 mPATH™-CRC Maintenance: The proportion of patients aged 50-74 who are eligible for CRC screening who complete mPATH™-CRC or have risk factors identified by mPATH™-CheckIn in months 7-12
- 5.3.7 mPATH™-CheckIn Reach: The proportion of patients aged 18 or older who complete mPATH™-CheckIn in months 1-6; this outcome will be calculated overall and within socioeconomic strata
- 5.3.8 mPATH™-CheckIn Adoption: The mean usage of mPATH™-CheckIn among staff and providers over the first 6 months following implementation; usage is calculated for front desk staff as the proportion of times mPATH™-CheckIn is completed out of the total times mPATH™-CheckIn should have been handed out; usage is calculated for nurses/providers as the proportion of times mPATH™-CheckIn is completed and data is transmitted to the EHR out of the total times mPATH™-CheckIn should have been handed out
- 5.3.9 mPATH™-CheckIn Acceptability, Appropriateness, and Feasibility: Mean AIM, IAM, and FIM scores for mPATH™-CheckIn as assessed on the 6-month clinic personnel survey

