Appendix B – Data Collection Instruments

The following instruments have been submitted to the IRB as pdf files:

Clinic Characteristics Survey

Clinic Staffing Form

Staff Linkage Form

Staff Consent & Contact Information Form

Staff Baseline Survey

Staff Demographics Survey

Clinic Support Log

Follow-Up Clinic Personnel Survey: 6 month timepoint

Follow-Up Clinic Personnel Survey: 12 month

Additional data collection instruments in development:

The final data collection instruments listed below have not yet been developed. Each instrument will be submitted to the IRB for formal review and approval before they are used with any human subjects. The planned data collection instruments and their descriptions are listed below.

Cost Database

All technology costs associated with implementing and maintaining mPATH will be recorded in a secure, electronic database.

mPATH-CRC Database

The mPATH-CRC database will be stored in an encrypted, HIPAA-compliant Cloud-based server with continuous data backup. The database is password protected and meets HIPAA security requirements. The database includes patient medical record numbers, date and time of use, and answers to mPATH-

EFFECTIVENESS AND IMPLEMENTATION OF MPATH-CRC: A MOBILE HEALTH SYSTEM FOR

COLORECTAL CANCER SCREENING

Wake Forest Baptist Comprehensive Cancer Center (WFBCCC)

WFBCCC # TBD

CRC survey questions (CRC screening history, CRC screening decisions, etc.). The database is password protected and access is limited to those with authorization. When the mPATH-CRC database is queried to construct our study dataset, the medical record numbers will be replaced with an anonymous study identifier by an honest broker. A full copy of the mPATH-CRC survey will be submitted to the IRB for review and approval prior to use with human subjects.

Clinic Query Database

We will query the study clinics' electronic health records and appointment systems to collect the following data elements needed for our planned analyses. Data will be collected for the time periods specified in the Experimental Methods (Section 4.0).

- Patient age
- Patient gender
- Patient race/ethnicity
- Flagged as needing a language interpreter (and language needed)
- Patient marital status
- Patient health insurance
- Patient history of colorectal cancer
- Patient history of colorectal polyps
- Patient family history of colorectal cancer
- Date of visit to clinic
- Name of provider being seen
- Name of nursing staff who roomed the patient

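### Staff-survey respondents are identified through clinic champions, whom Table 1 gives only to high-touch clinics; no rule covers low-touch clinics or the 6-month survey, so selection can differ by arm.

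*Combined protocol and SAP*

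**What the plan says.** **Who is surveyed at baseline (4.4.6).** The survey is given at the kick-off training visit to all clinic personnel "who are involved with the implementation of mPATH-CRC, as identified by the local clinic champions". Administrators, nurses and providers are the examples named. No arm is specified.

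**Who has a champion (Table 1, 4.4.1, 4.4.2).** The pre-implementation row of Table 1 reads "Clinic champion identified" for high touch and N/A for low touch. In the high-touch description, the kick-off is a "training session for clinic staff identified by the local clinic champion". The low-touch description offers the same kick-off session and materials plus support on request. It names no champion, "nor will study staff proactively reach out to them after the kick-off training session".

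**Who is surveyed later (4.4.6).** Follow-up surveys are set at 6 and 12 months after the on-site training. The text gives their timing and content but no rule for who receives them. Personnel with no baseline survey, such as new hires, complete it with their first follow-up survey.

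**What the survey feeds (5.3.4, 5.3.9, 6.3).** AIM, IAM and FIM scores for mPATH-CRC and mPATH-CheckIn are secondary outcomes, "as assessed on the 6-month clinic personnel survey". Section 6.3 compares continuous staff-level outcomes between arms with linear mixed models: arm as the main predictor, site as a random effect and clinic size as a covariate.

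**A conflicting passage (4.6).** The mixed-methods section counts a champion among the four people to be interviewed in each clinic, and adds: "The clinic champion will assist in the identification of the other team members for interviews".

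**The concern.** The only stated way of finding survey respondents runs through a person who, on the natural reading of Table 1, is part of the high-touch intervention. In high-touch clinics that person guides the rollout and is chosen partly for an ability to promote a project. In low-touch clinics someone else must draw up the list, or nobody does, and the plan does not say which.

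AIM, IAM and FIM measure how staff regard the program. If one arm's list leans towards staff who are more engaged with it, the arm means can differ with no true effect of the strategy on staff opinion. The list is drawn up after allocation and by a route that depends on allocation, so randomising the clinics does not protect this comparison.

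**Working it through.** The documents give no sample size, standard deviation, target difference or power for AIM, IAM or FIM, so there is no figure to reproduce. The check compares the relevant sections.

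**Step 1: can the rule be applied in both arms?** Section 4.4.5 allocates one clinic of each pair to each strategy, so 22 / 2 = 11 clinics per arm.

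| Question | High touch (11 clinics) | Low touch (11 clinics) |
|---|---|---|
| Champion before launch (Table 1) | Yes | N/A |
| Who names the kick-off attendees | Champion (4.4.1) | Not stated (4.4.2) |
| Provider training at kick-off (Table 1) | Listed | Not listed |
| Who identifies baseline respondents (4.4.6) | Champion | Champion named in the rule, none assigned |
| Frame for the 6-month survey (4.4.6) | Not stated | Not stated |

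The rule works in one arm only. Two further rows point the same way. The baseline survey is given at the kick-off, yet providers, who are named as survey respondents, have a listed training session there only under high touch. High touch also creates super-users and an alternate champion, roles not listed for low touch. Being involved with implementation may therefore itself mean something different in each arm.

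**Step 2: does this reach the 6-month scores?** The champion clause belongs to the baseline paragraph. The follow-up paragraph names no new frame, and 4.4.6 treats follow-up respondents without a baseline survey as the exception. The simplest reading is that follow-up returns to the baseline group and adds new hires. If that is right, the arm-dependent rule carries forward. If it is wrong, the survey that supplies the outcome has no respondent definition in either arm.

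**Step 3: can the model correct it?** Suppose the list in arm *a* covers a fraction *f_a* of the involved staff, everyone listed responds, and the staff left off score *d_a* lower on average than those listed. Then

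- mean of all involved staff = mean of listed staff − (1 − *f_a*) × *d_a*
- bias in the arm mean = (1 − *f_a*) × *d_a*
- bias in the arm difference = (1 − *f_H*) × *d_H* − (1 − *f_L*) × *d_L*

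The site effect in 6.3 describes variation between clinics around their arm's mean, and clinic size is the matching factor. Neither carries information on who was asked. A shift common to one arm's clinics goes into the arm coefficient.

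The bias is zero when both lists are complete, or when the two terms happen to be equal. It falls as coverage rises, but not when more respondents are recruited through the same partial list. None of *f_H*, *f_L*, *d_H* and *d_L* is in the documents.

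**The case against.** The strongest reply has four parts.

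- **The clause governs the baseline survey, not the survey that yields the scores.** This is correct, and it narrows the point. It does not remove it, because the 6-month survey has no stated frame.
- **The text asks for all involved personnel.** A reader might infer that an advocate hand-picks favourable respondents. The documents do not say that: the champion supplies a list meant to be complete. What remains is that the champion decides who counts as involved.
- **Low-touch clinics may have a champion after all, since 4.6 expects one in each clinic.** That contradicts Table 1. It makes the absence of low-touch champions the better reading rather than a certainty, and the passages need reconciling whichever is meant.
- **Forms not reproduced in the document may already define the roster.** Appendix B lists a "Clinic Staffing Form" among instruments sent to the IRB. Its content and timing are not shown, so it may hold a common roster, but nothing in 4.4.6 says that it is used this way.

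Two further inferences are tempting. One is that the organisational-culture covariate in 6.2 is affected too, but 6.2 does not say that it comes from this survey. The other is that the 4.6 interviews need the same frame. Those are qualitative, run to thematic saturation, and carry no statistical comparison between arms.

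**Conclusion.** The point holds as a risk of selection that differs by arm. A reader might go further and conclude that the two arms will in fact be compared on differently selected samples. The documents do not support that, because low-touch and 6-month selection are left undefined rather than defined differently.

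The conclusion rests on two readings: that Table 1 and 4.4.2 govern over 4.6 on who has a champion, and that the follow-up surveys return to the baseline group plus new hires. If the second reading fails, the gap is a missing frame in both arms.

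The size cannot be determined from the documents. A tendency to favour high touch is plausible, but a manager drawing up the low-touch list could select in the same way and offset part of it.

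What is affected is AIM, IAM and FIM in 5.3.4 and 5.3.9. The primary Reach outcome counts eligible patients, so staff-survey selection does not touch it. The point is worth correcting because the remedy is cheap and no later modelling under 6.3 can replace it.

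**What to change.** 1. In 4.4.6, delete the closing clause that leaves identification to the champions.
2. Define one frame for both arms at baseline, 6 and 12 months: all staff in check-in, rooming, provider and manager roles, plus new hires in those roles. Take it from the Clinic Staffing Form if that form holds such a roster. If it does not, collect the roster in the same way in every clinic.
3. Report survey response rates by arm and by role alongside the AIM, IAM and FIM comparisons.
4. Reconcile 4.4.6 and 4.6 with Table 1 on whether low-touch clinics have a champion.

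The cost is protocol wording and a few more $10 survey incentives. The downside is that some less-involved staff will be invited.
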